#### 4. STATISTICAL METHODS

# 4.1. Sample Size Justification

In the PA21 treatment group, assuming a mean change in serum phosphorus levels from baseline to end of Stage 1 of 1.2 mg/dL, a standard deviation for the change of 2.0 and to further allow for an approximate drop-out rate of 30%, 100 randomised subjects will provide more than 90% power.

The sample size estimation is based on conservative values from the Phase 3 study, and performed using nQuery Version 6.0.

One hundred subjects should also be sufficient to provide robust safety and dosing information for PA21 in the paediatric and adolescent subjects with CKD.

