#### 5. CHANGES TO PLANNED ANALYSES

To take into consideration covariate factors for the evaluation of the primary endpoint, baseline serum phosphorus, age (in categories) at randomisation, region and gender, a mixed model will be used in replacement to the paired t-test mentioned in the protocol.

Following discussions and agreements with PDCO and FDA, the following new age classification at randomisation will be used for the outputs: 0 to <1 year/ $\geq$ 1 year to <6 years/ $\geq$ 6 years to <12 years/ $\geq$ 12 years to <18 years.

Due to difficulties in the recruitment of patients below 9 years of age, PDCO agreed to reduce required minimum numbers of recruited patients as follows:

At least 60 subjects must be randomised into PA21 group and the following number of subjects from each age group as detailed below:

- Less than 1 year: no minimum number of randomised patients
- From 1 to less than 6 years: at least 5 patients on PA21
- From 6 to less than 12 years: at least 10 patients on PA21
- From 12 to less than 18 years: at least 10 patients on PA21
- Phoslyra arm: no minimum number of randomised patients.

Furthermore, FDA agreed that a partial waiver of PREA study requirements in patients less than 2 years of age can be justified on the basis that necessary studies are impossible or highly impracticable. The Agency also believes that it may be possible to generalize the findings in older paediatric patients down to younger patients greater than 2 years of age, indicating that the study can be completed without the need to recruit originally required minimum numbers of patients below 9 years of age.

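### Section 4.1 justifies power and safety for 100 PA21 subjects, but Section 5 requires only 60 and changes the test: the plain mean change keeps over 90% power, the test as coded is not guaranteed it

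*SAP*

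**What the plan says.** Section 4.1 sizes the PA21 arm by "assuming a mean change in serum phosphorus levels from baseline to end of Stage 1 of 1.2 mg/dL", with an SD of 2.0 for that change and 30% drop-out, and concludes that "100 randomised subjects will provide more than 90% power". It does not name the test. It adds that "One hundred subjects should also be sufficient to provide robust safety and dosing information for PA21". Sections 2.1 and 2.2 give the same target of about 100 on PA21, and Table 1 lists age minima for that design.

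Section 5 changes both inputs:

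- Size: "At least 60 subjects must be randomised into PA21 group". The age minima become "From 1 to less than 6 years: at least 5 patients on PA21", then 10 from 6 to under 12 years and 10 from 12 to under 18. There is no minimum below 1 year.
- Test: "a mixed model will be used in replacement to the paired t-test mentioned in the protocol".

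Section 4.7.1 fits that model to PA21 subjects only. Age, region and gender are class effects and baseline phosphorus is a covariate. It tests the treatment LSMEANS with no weighting option. Under Section 4.2.1 the primary endpoint is the only one with a planned formal test, two-sided at 5%. The SAP gives no power for 60 subjects or for the model, and its document history lists no revision of Section 4.1.

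**The concern.** Sections 4.1 and 5 are both in force and describe different trials. The printed power belongs to a size that is no longer required and, as far as Section 5 shows, to a test that is no longer used.

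The change of test matters because unweighted LSMEANS give each class level the same weight however few children it holds. With three occupied age classes, a class of four or five children carries one third of the age weight and inflates the standard error. The calculation in 4.1 makes no allowance for this.

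At stake is how the only planned formal test and the safety database will be read. A non-significant result, or a sparse adverse-event table, would be judged against a justification that the current plan does not guarantee.

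**Working it through.** **Inputs from the SAP.** Mean change 1.2 mg/dL, SD of the change 2.0 and drop-out 30% (4.1); two-sided 5% (4.2.1); at least 60 on PA21 with age minima 5/10/10 (Section 5); model and LSMEANS statement (4.7.1).

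**Assumptions, not in the SAP.** The region split, an even gender split, the age mix beyond the minima, and the residual SD after adjustment. Three age classes are taken as occupied, because the document history notes that the first age group is empty.

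**1. The plan's own figure.** One-sample t-test, SE = SD/√n, noncentrality = 1.2/SE, n − 1 degrees of freedom.

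- n = 100 × 0.7 = 70: SE = 2.0/√70 = 0.239, noncentrality 5.02, power 99.9%. The printed claim reproduces with a wide margin.

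**2. The same test at 60 randomised.**

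- n = 60 × 0.7 = 42: SE = 2.0/√42 = 0.309, noncentrality 3.89, power 96.7%.
- Power of 90% needs 32 evaluable, or 32/0.7 = 45.7, so 46 randomised.

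**3. The test as coded, age weighting only.** With equal weight on three age classes, Var = (SD²/9) × Σ(1/n_k). Put 60 at the minima for the two younger groups and the rest in the oldest: 5/10/45. After 30% loss this is about 4/7/31.

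- Var = (4/9) × (1/4 + 1/7 + 1/31) = (4/9) × 0.425 = 0.189, so SE = 0.435 against 0.309 for the plain mean.
- Noncentrality = 1.2/0.435 = 2.76, with 42 − 3 = 39 degrees of freedom: power about 77%.

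**4. The full model.** With region, gender and baseline added, Var = σ² × L(X′X)⁻¹L′, where L puts equal weight on each level. Power is averaged over random allocations of region, gender and baseline.

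| Ages | Regions (assumed) | Residual SD 2.0 | SD 1.8 | SD 1.6 |
|---|---|---|---|---|
| 4/7/31 (n=42) | 21/21 | 75% | 83% | 91% |
| 4/7/31 | 29/13 | 71% | 80% | 88% |
| 4/7/31 | 25/13/4 | 61% | 70% | 80% |
| 5/10/45 (n=60) | 30/30 | 87% | 93% | 97% |
| 5/10/45 | 42/18 | 84% | 90% | 96% |
| 5/10/45 | 36/18/6 | 76% | 84% | 91% |
| 7/12/23 (n=42) | 21/21 | 92% | 96% | 99% |
| 10/12/20 (n=42) | 16/16/10 | 94% | 97% | 99% |
| 14/14/14 (n=42) | 21/21 | 97% | 99% | over 99% |

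The three-region rows keep Rest of the World at about 10% (4/42 and 6/60), above the 5% that Section 4.2.6 gives as its example for pooling.

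**5. Like for like at 100 randomised.** The coded test at 70 evaluable, residual SD 2.0 and four assumed age classes:

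- ages 3/7/20/40: 88% with regions 35/35, about 69% with 33/33/4;
- ages 4/10/20/36: 91% with regions 30/30/10.

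**6. Safety.** The event rate seen at least once with 95% probability is 1 − 0.05^(1/n): 3.0% at n=100 and 4.9% at n=60. For a 3% event, the chance of seeing at least one is 1 − 0.97^n: 95% at n=100 and 84% at n=60.

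**The case against.** The strongest reply is that 4.1 contains no arithmetic error and that Section 5 openly records the reduced minima and the new test. Both are true. Disclosure in Section 5 still leaves 4.1 stating a power and a safety adequacy for a size that the plan no longer requires.

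Four stronger readings are tempting, and the document does not support them.

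- *That cutting to 60 leaves the trial underpowered.* It does not: the plain mean change keeps 96.7%, and 46 randomised would be enough for 90%.
- *That the shortfall comes from the smaller number.* It comes from equal weighting over sparse levels. Step 5 shows that the same weighting can bring the coded test below 90% at 100 randomised.
- *That the primary test has 60-75% power.* This holds only if several conditions coincide. Sixty is a floor, and 2.1 and 2.2 still say about 100. The younger groups would have to sit at their minima. The full 30% would have to be lost, although the FAS needs only one dose and one post-baseline value, and 4.2.8.1 uses the last available Stage 1 value. The residual SD would have to stay at 2.0, although 4.1 gives that figure for the unadjusted change. Flatter age mixes give 92-97%.
- *That safety rests on 42 children.* The Safety Population in 3.1 is everyone dosed, so the comparison is 100 with 60.

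It is also an inference from Section 5, not a statement in 4.1, that the printed power was computed for a paired t-test.

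**Conclusion.** The point holds in limited form. Section 4.1 does not describe the enrolment and test that Section 5 puts in force, and it should be restated.

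The claim of more than 90% survives the cut to 60 for the unadjusted PA21 mean change (96.7% at n=42). It is not assured for the equally weighted LS-mean. At the Section 5 minima with residual SD 2.0, that test has about 60-75% at n=42 and about 76-87% with all 60 evaluable. Balanced ages with two equal regions give about 97%, and a smaller residual SD raises every figure. These ranges rest on assumed region splits, age mix and residual SD, so they show what the plan permits and do not forecast the result.

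The safety figures need no model assumption: the rate detectable with 95% probability goes from 3.0% to 4.9%.

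**What to change.** Before database lock:

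- Restate 4.1 for the PA21 minimum of 60 (42 after 30% drop-out). Attach the over-90% claim explicitly to the unadjusted PA21 mean change, with 96.7% at n=42.
- Either report that mean with its t-based 95% CI and p-value alongside the model, or pre-specify LSMEANS with observed-margin weights (the OM option). In this main-effects model the observed-margin LS-mean has SE = residual SD/√n, which is 0.309 at SD 2.0 and n=42, so sparse levels no longer inflate it.
- Say in 4.1 that the power of the equally weighted LS-mean depends on the age and region mix and can fall below 90%.
- In the safety sentence, replace one hundred with 60 and give the detectable event rate (4.9%, against 3.0% at 100). Do not use 42 for safety.
- Cross-refer 2.1, 2.2 and Table 1 to the Section 5 minima.

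The cost is SAP wording and one extra summary line or one code option, with no additional patients. The stated power and safety precision become slightly less favourable.

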# 4.2. General Statistical Methods and Data Handling

#### 4.2.1. General Methods

All outputs will be incorporated into rtf files, sorted and labelled according to the International Conference on Harmonisation (ICH) recommendations, and formatted to the appropriate page size(s).

For all outputs, the order and labelling of the treatment groups will be maintained as shown below:

#### 1. PA21

## 2. Phoslyra

A 'Total' column will be used in all the outputs, which will present a total over both treatment groups, with the exception of exposure data where data will be presented separately for each drug.

Tabulations will be produced for appropriate demographic, baseline, efficacy and safety parameters. For categorical variables, summary tabulations of the number and missing observations as well as the number and percentage within each category of the parameter will be presented. For continuous variables, the number and missing observations, mean, median, standard deviation, Q1, Q3, minimum, and maximum values will be presented.

For the laboratory parameters, the number of the decimal places (dp) will be determined using the following rules based on the number of dp from the raw data:

- mean, median, q1 and q3 = raw + 1
- sd = raw + 2
- Min and max = raw

Formal statistical hypothesis testing will be performed on the primary endpoint only with test conducted at the 2-sided, 0.05 level of significance. Summary statistics will be presented, as well as confidence intervals on selected parameters, as described in the sections below. Some other statistical tests within each group may be performed for the secondary efficacy endpoints depending on the observed clinical differences.

Baseline will be defined as the latest measurement collected prior to first dose of study treatment.

Stage 1 data will be defined as all data collected until the last visit in the titration phase (prior to visit 12 and when "Yes" is responded to the question "Will subject enter the Stage 2 Safety Extension period after the current visit?"). Of note, if subject withdrew during stage 1 (i.e. no stage 2 initiated), visit 16 will be considered as part of stage 1.

Stage 2 data will be defined as all data collected from the day after the last visit in the titration phase.

Both local and central laboratory data will be reported using SI units, unless otherwise specify.

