# 4.2.5. Multiple Comparisons/Multiplicity

Multiplicity is not of concern for this study with a single primary efficacy endpoint.

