## 4.7.2. Secondary Efficacy Endpoints

For the following secondary endpoints, summary statistics with 95%CIs for the mean change will be provided by treatment group using the same linear mixed model as for the primary efficacy endpoint:

- Change in serum phosphorus levels from baseline to the end of Stage 1 in Phoslyra group
- Change in serum phosphorus levels from baseline to the end of Stage 2 in both groups

The above secondary endpoints are based on central laboratory data; in case of missing data regarding central laboratory data, local laboratory measurements are used (please refer to Sections 4.2.8.1 and 4.2.8.2 for the imputation to be applied).

Serum phosphorus values over time will be summarised by treatment group using descriptive statistics based both on central and on local laboratory measurements, separately.

Box plots will be generated for the change in serum phosphorus levels from baseline for each treatment arm to the end of Stage 1 and to the end of Stage 2 on the FAS and PPS Populations.

In addition, plots will be provided with one curve for each treatment arm representing the mean change (±standard error of the mean (SEM)) from baseline in serum phosphorus levels at each time point to the end of Stage 1 and to the end of Stage 2 for the FAS and PPS Populations.

For the following secondary endpoints based on both central and local laboratory measurements, number and percentage calculated using the number of subjects with non-missing serum phosphorus level as denominators with corresponding exact 95%CIs will be provided by treatment group:

- Subjects with serum phosphorus level within the age related target range at each visit
- Subjects with serum phosphorus level within the age related normal range at each visit.

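### SAP 4.2.1 lets optional within-group tests on secondary efficacy endpoints be chosen from the observed differences, with no endpoint, trigger, alpha or exploratory label fixed

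*SAP*

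**What the plan says.** Section 4.2.1 (General Methods) sets the scope of testing: "Formal statistical hypothesis testing will be performed on the primary endpoint only with test conducted at the 2-sided, 0.05 level of significance". Two sentences later, in the same paragraph, it adds: "Some other statistical tests within each group may be performed for the secondary efficacy endpoints depending on the observed clinical differences".

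Section 4.2.5 disposes of multiplicity in one line: "Multiplicity is not of concern for this study with a single primary efficacy endpoint".

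Section 4.7.2 names no test for the secondary endpoints. For the changes in serum phosphorus, "summary statistics with 95%CIs for the mean change will be provided by treatment group", from the mixed model used for the primary endpoint. The changes are "Change in serum phosphorus levels from baseline to the end of Stage 1 in Phoslyra group" and "Change in serum phosphorus levels from baseline to the end of Stage 2 in both groups". Percentages in the age-related target and normal ranges are given by visit and treatment group with exact 95% confidence intervals.

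Section 5 (Changes to Planned Analyses) does not mention extra tests. Elsewhere the SAP rules testing out explicitly where it means to: Section 4.5 for baseline characteristics and Section 4.9.1 for adverse event rates.

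**The concern.** The difference that would be tested also decides whether it is tested. That is a rule for selecting results, and it is written into the plan. Nothing limits it: no endpoint, test, threshold, significance level or label is given. A reader of the study report could not tell how many differences were inspected before a given p-value appeared.

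The secondary changes bear on two stated objectives in Section 1.2: maintenance of the PA21 effect to the end of Stage 2, and the efficacy of Phoslyra. Section 4.7.2 applies the primary mixed model to them, and Section 4.7.1 already takes a t-test p-value from that model. P-values for the secondary changes will therefore be easy to produce, and the sentence lets the look of the data decide which are shown.

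**Working it through.** **Is there a figure in the plan to reproduce?** The SAP gives no error rate for the secondary tests. Its only related figure is the power in Section 4.1: mean change 1.2 mg/dL, SD of change 2.0, about 30% drop-out, 100 randomised, more than 90% power. With n = 100 × (1 − 0.30) = 70, a two-sided one-sample t-test at 0.05 has power 99.9%, so the statement reproduces. The present point does not depend on it; only the SD and the drop-out rate are reused below.

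**Which contrasts have an obvious within-group null (zero change)?** There are three in Section 4.7.2: Phoslyra at end of Stage 1, PA21 at end of Stage 2, Phoslyra at end of Stage 2.

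**Familywise error if all three nulls hold and each test is at 0.05, unadjusted**
- Independent tests: 1 − 0.95³ = 1 − 0.8574 = 14.3%.
- Any dependence (Bonferroni bound): 3 × 0.05 = 15%.
- Simulation, testing only the largest of three independent contrasts (200,000 replicates): 14.2%.

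Running only some of the three tests cannot take the overall rate above 15%.

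**Effect of the selection step on one contrast.** The SAP states no trigger, so the trigger c is an assumption, varied below. The test is run only if the absolute observed mean change is at least c. Data are normal with true mean change 0 and SD 2.0 mg/dL, analysed by a one-sample t-test at two-sided 0.05, with 200,000 simulated trials per n. The sample sizes are n = 21 for Phoslyra (30 × 0.70) and n = 70 for PA21. Section 4.1 states the 30% drop-out for PA21 only, so applying it to Phoslyra is also an assumption.

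| n | c (mg/dL) | Test is run | p < 0.05, given it is run | Run and p < 0.05 |
|---|---|---|---|---|
| 21 | 0.25 | 56.7% | 8.8% | 5.0% |
| 21 | 0.50 | 25.2% | 19.8% | 5.0% |
| 21 | 0.75 | 8.6% | 52.3% | 4.5% |
| 21 | 1.00 | 2.2% | 90.5% | 2.0% |
| 70 | 0.25 | 29.3% | 16.8% | 4.9% |
| 70 | 0.50 | 3.6% | 94.1% | 3.4% |

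The fourth column shows the damage. Among tests that were run because the difference looked large, a p-value under 0.05 is far more common than 5% even with no true change. The last column shows the limit: for a single contrast, the overall chance of both testing and rejecting never exceeds 5%.

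**The case against.** Much of the case on the other side stands.

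- **Contradiction.** A reader might infer that the paragraph contradicts itself. The word formal in "Formal statistical hypothesis testing will be performed on the primary endpoint only" allows a consistent reading: one formal test, plus optional informal ones. The SAP never says that the extra tests are informal, so the text is unclear and needs reconciling, but a flat contradiction is not established.
- **Multiplicity statement.** A reader might infer that Section 4.2.5 is wrong. It rests on there being one primary endpoint, which is sound for the confirmatory error rate. Nothing in the sentence touches the primary test or its alpha.
- **Invalid p-values.** A reader might call every such p-value invalid. As the last column of the table shows, that holds only conditional on selection or across a family of contrasts.
- **A much larger error rate.** The by-visit percentages (two ranges, two arms, 11 post-baseline analysis visits in Section 4.2.9: 2 × 2 × 11 = 44 cells) might suggest a pool well above ten. Ten independent tests would give 1 − 0.95¹⁰ = 40.1%. The SAP does not support that figure. The cells come from the same subjects measured repeatedly, the ranges in Tables 4 and 5 overlap heavily, and for entries such as "Subjects with serum phosphorus level within the age related target range at each visit" Section 4.7.2 states no null value.
- **Little practical harm.** Section 4.7.2 gives 95% confidence intervals for all three change contrasts whatever is observed, and Section 7.1 lists the tables in advance, so an unfavourable estimate cannot be hidden. A 5% test of zero change from the same model says no more than whether the interval excludes zero. Removing the p-values therefore leaves three unadjusted intervals.

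The tests are also optional, and Section 1.1 describes the comparison with Phoslyra as descriptive. These points limit the consequence. They do not remove the fault, because the SAP still states that the results decide what is tested and gives no label to warn the reader.

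**Conclusion.** The point holds in a limited form. Section 4.2.1 states a data-driven rule for secondary tests, and no other section fixes its scope or status. For the three secondary change contrasts, unadjusted 5% testing carries a familywise error of about 14% if independent and at most 15% under any dependence, assuming that all three nulls are true. The conditional rates in the table show the direction of the effect but have no single size, because the trigger, the evaluable Phoslyra number and the simple t-test are assumptions. They also take the natural reading that a larger observed difference is what prompts a test.

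The primary analysis, its 0.05 level and the planned intervals are not affected. What is at risk is the interpretation of any secondary p-value that appears in the report. The sentence should be corrected, but it is no threat to the main conclusion.

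**What to change.** Delete the sentence on further within-group tests from Section 4.2.1. State there, or in Section 4.7.2, that the secondary efficacy endpoints are reported with the estimates and 95% confidence intervals already planned, and that these are descriptive and not adjusted for multiplicity. The second part is needed because three unadjusted intervals invite the same reading as three unadjusted tests. Add that any test run later will be labelled post hoc and exploratory, with the number of tests run.

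If the sponsor wants secondary p-values, the alternative is to name the three change contrasts in advance with a multiplicity rule. Bonferroni at 0.05 / 3 = 0.0167 each would keep the familywise error at or below 5%.

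The recommended change costs one deleted sentence and two short statements, with no new data or analyses. The sponsor gives up unplanned secondary p-values.

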## 4.2.2. Computing Environment

All descriptive statistical analyses will be performed using SAS statistical software (Version 9.4 or later), unless otherwise noted. Medical History and adverse events will be coding using MedDRA (version 19.1 or later). Concomitant medications will be coded using World Health Organisation (WHO) Drug Dictionary (version June 2016 or later).

### 4.2.3. Methods of Pooling Data

Not applicable to the present study.

#### 4.2.4. Adjustments for Covariates

The primary and secondary efficacy endpoints including change in serum phosphorus levels from baseline will be analysed through a linear mixed model with baseline serum phosphorus value, age (in categories) at randomisation, region and gender as covariates.

